Section 1.1 Synopsis; Section 4.1 Overall Design; Section 8.3 Adverse Events and Serious Adverse Events; Section 9.2.1 Sample Size Determination; Appendix A3 Informed Consent Process; Appendix G Guidelines for Evaluation of Objective Tumour Response Using RECIST 1.1 (Response Evaluation Criteria in Solid Tumours)	The new appendix, Appendix K1.3, was cross-referenced to indicate country-specific requirements for Germany.	For document navigation.
Section 1.1 Synopsis Section 7.1.2 Follow-up of Patients Post Discontinuation of Study Treatment	Corrected time period of follow-up for safety assessments post treatment discontinuation from "90 days" to "180 days" after last dose of study treatment for ceralasertib and durvalumab combination.	Correction.

Section Number and Name	Description of Change	Brief Rationale
Section 4.4 End of Study Definition	Clarified definition of the end of study according to EU and FDA requirements.	For consistency and alignment in terms of posting study results.
Section 5.1.1 Inclusion Criteria, Main Study and Biopsy Sub-Study; Section 5.3.1 Contraception	Updated the contraception period after the last dose of study intervention for female patients from 1 month to 6 months. Added a restriction that female patients must not breastfeed and must not donate or retrieve ova from signing the ICF to approximately 6 months after the last dose of study treatment.	To align with the latest safety outcomes and recommendations for contraception.
Section 6.5.2 Drug-Drug Interaction Between Ceralasertib and Other Drugs; Appendix F Guidelines Regarding Potential Interactions of Ceralasertib with Concomitant Medications, including the table listing drugs known to be metabolised by	Addition of ceralasertib as a potential inducer of CCI.	To align with the current ceralasertib IB, edition 13, dated 18 September 2024.
Section 6.6.1 Management of Toxicities	Added guidance on management of prolonged haematological toxicities	To align with Sponsor's guidance ceralasertib toxicity management updated consequence to including MDS/AML as potential risks.
Section 6.7 Treatment After the End of the Study; Section 8.3.1 Time Period and Frequency for Collecting AE and SAE information	Added wording related to PTAP.	To clarify the planned safety data collection and reporting during the PTAP.
Section 8.3.7 Disease Progression	Added text on reporting of disease progression as a safety event in applicable cases.	For clarification.

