1.3 Schedule of Activities

The procedures for this study are presented in the SoA for ceralasertib and durvalumab combination therapy in Table 1, for the ceralasertib monotherapy in Table 2, and for the biopsy sub-study in Table 3.

 Table 1
 Ceralasertib Plus Durvalumab (Main Study)

Procedure	Screening a			Inte	rvention	period	(28-day	cycles)				Post-in	tervent	ion follo	ow-up peri	iod	Details in CSP section or appendix
	Scr		Cycl	es 1-2			Cycle 3	3	C4-on	wards	ntinued tment)	(# (-	/ follow- after las	_	al til W)	
Cycle Day	-21 to -1	Day 1	Day 7	Day 8	Day 15	Day 1	Day 7	Day 8	Day 1	Day 8	Study Treatment Discontinued (last dose of study treatment)	30 days	60 days	90 days	180 days (6 months)	Progression/Survival Follow-up (Q8W until 18 months, then Q12W)	
Visit window (± days)	-	-	-	-	± 1	± 3	-	± 1	± 3	± 1	Study Tr (last dos	± 3	± 7	± 7	±7	Prog Follo 18 mo	
Informed consent: main study ^b	X																Section 5 and Appendix A 3
Informed consent: genetic sample and analysis (optional) ^b	X																Section 5.1 and Appendix A 3
Archival tumour sample, mandatory ^c	X																Section 8.6.1
Fresh tumour biopsy	X				X (C2 only)						X (PD)						Section 8.6.1
Inclusion and exclusion criteria e, f	X	X															Sections 5.1, 5.2 and 5.4
Demography ^g	X															_	Section 5.1

Procedure	Screening a			Inte	rvention	period	(28-day	cycles)				Post-in	tervent	ion follo	w-up peri	iod	Details in CSP section or appendix
	Ser		Cycl	es 1-2			Cycle 3	}	C4-on	wards	ntinued tment)	(# (y follow- after las	-	al (til W)	
Cycle Day	-21 to -1	Day 1	Day 7	Day 8	Day 15	Day 1	Day 7	Day 8	Day 1	Day 8	Study Treatment Discontinued (last dose of study treatment)	30 days	60 days	90 days	180 days (6 months)	Progression/Survival Follow-up (Q8W until 18 months, then Q12W)	
Visit window (± days)	-	-	-	-	± 1	± 3	-	± 1	± 3	± 1	Study Tr (last dos	± 3	± 7	± 7	±7	Prog Follo 18 ma	
Prior anti-cancer therapy h	X																Section 5.1
Full physical examination ^a	X	X				X			X		X	X	X	X	X		Section 8.2.1
Targeted physical examination i				X	X			X		X							Section 8.2.1
Height	X																Section 8.2.1
Weight ^a	X	X		X		X		X	X	X	X	X	X	X	X		Section 8.2.1
Past and current medical conditions	X	X a															Sections 5.1 and 5.2
12-lead ECG ^{j, k}	X (Tri plic ate)			As	clinically	indicate	d; singl	e ECGs									Section 8.2.3
Echocardiogram/MU GA	X				As cli	nically in	ndicated	1			X						Section 8.2.6.1
Vital signs ^k	X	X	X	X	X	X	X	X	X	X	X	X	X	X	X		Section 8.2.2

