7.1.2 Follow-up of Patients Post Discontinuation of Study Treatment

After study treatment discontinuation, all patients will be followed up for safety assessments 30 days after their last dose of study treatment for ceralasertib monotherapy or 180 days after last dose of study treatment for ceralasertib and durvalumab combination (ie, the safety follow-up visit). Patients will also be followed for survival status and post discontinuation anti-cancer therapies. Additional assessments to be performed at the time of the safety follow-up are detailed in the SoA (Section 1.3). For country-specific requirements for Belgium and France see Appendices K 1.1 and K 1.2, respectively.

Patients who have discontinued study treatment prior to objective RECIST 1.1-defined radiological progression will be followed up with tumour assessments according to the SoA until RECIST 1.1 defined disease progression or death regardless of whether or not the patient started a subsequent anti-cancer therapy, unless they have withdrawn all consent to study related assessments.

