8.3.1 Time Period and Frequency for Collecting AE and SAE Information

Adverse events and SAEs will be collected from time of signature of ICF, throughout the treatment period and including the safety follow-up period (30 days after last dose of study treatment for ceralasertib monotherapy or 90 days after last dose of study treatment for ceralasertib and durvalumab combination).

If the investigator becomes aware of an SAE with a suspected causal relationship to the study treatment that occurs after the end of the clinical study in a patient treated by him or her, the investigator shall, without undue delay, report the SAE to the sponsor as described in Section 8.3.12.

For patients continuing in the PTAP, AEs and SAEs will be recorded by the treating physician from the time the participant signs informed consent and will continue throughout the program until the end of the PTAP or until consent has been withdrawn. Collection and reporting of AEs and SAEs after the final DCO is described in Section 8.3.11.

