8.3.9 Deaths

All deaths that occur during the study treatment period, or within the protocol-defined follow-up period after the administration of the last dose of study treatment, must be reported as follows:

• Death clearly resulting from disease progression should be documented in the eCRF in the Statement of Death page. It should not be reported as an SAE.

- Where death is not due (or not clearly due) to progression of the disease under study, the AE causing the death must be reported as an SAE within 24 hours. It should also be documented in the Statement of Death page in the eCRF. The report should contain a comment regarding the co-involvement of PD, if appropriate, and should assign the main and contributory causes of death.
- Deaths with an unknown cause should always be reported as an SAE and documented in the Statement of Death page in the eCRF, but every effort should be made to determine a cause of death. A post-mortem may be helpful in the assessment of the cause of death, and if performed, a copy of the post-mortem results should be forwarded to AstraZeneca Patient Safety or its representative within the usual time frames.

Deaths occurring after the protocol-defined follow-up period after the administration of the last dose of study treatment should be documented in the Statement of Death page. If the death occurred as a result of an event that started after the defined follow-up period and the event is considered to be due to a late-onset toxicity to study treatment, then it should also be reported as an SAE.

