After study treatment discontinuation, all patients will be followed up for safety assessments 30 days after their last dose of study treatment for ceralasertib monotherapy or 90 days after last dose of study treatment for ceralasertib and durvalumab combination. Patients will also be followed for survival status and post discontinuation anti-cancer therapies. A urine pregnancy test must also be performed for WOCBP 6 months after last dose of study treatment (ceralasertib monotherapy or ceralasertib in combination with durvalumab). Additional assessments to be performed at the time of the safety follow up are detailed in the SoA (Section 1.3).

Section 8.3.13.2 (Paternal Exposure)

Revised text

Pregnancy in a patient's partner(s) is not considered to be an AE. However, the outcome of all pregnancies (spontaneous miscarriage, elective termination, ectopic pregnancy, normal birth or congenital anomaly), occurring from the date of the first dose until 180 days after the last dose and as indicated by previous studies (preclinical and clinical) should, if possible, be followed up and documented in the medical record and provided to the AstraZeneca Patients Safety data entry site. Consent from the partner must be obtained before the information is collected and reported to AstraZeneca via the Pregnancy Report Form.

K 1.2 Country-specific Requirements for France

Section 1.1 (Synopsis)

Revised text

After study treatment discontinuation, all patients will be followed up for safety assessments 30 days after their last dose of study treatment for ceralasertib monotherapy or 90 days after last dose of study treatment for ceralasertib and durvalumab combination. A urine pregnancy test must be performed for WOCBP at 6 months after their last dose of study treatment (ceralasertib monotherapy and ceralasertib in combination with durvalumab). All randomised patients in the main study and all patients in the biopsy sub study will be followed for survival status and post discontinuation anti-cancer therapies.

Revised table

Procedure	Screening a		Intervention period (28-day cycles) Post-intervention follow-up period													iod	Details in CSP section or appendix
	Scr		Cycl	es 1-2		Cycle 3 C4-onwards						Safety follow-up (# of days after last dose) the state of the state					
Cycle Day	-21 to -1	Day 1	Day 7	Day 8	Day 15	Day 1	Day 7	Day 8	Day 1	Day 8	ntment of stud	30 days	60 days	90 days	6 months	Progression/Survival Follow-up (Q8W until 8 months, then Q12W)	

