Section 7.1.2 (Follow-up of Patients Post Discontinuation of Study Treatment)

Revised text

After study treatment discontinuation, all patients will be followed up for safety assessments 30 days after their last dose of study treatment for ceralasertib monotherapy or 90 days after

last dose of study treatment for ceralasertib and durvalumab combination. Patients will also be followed for survival status and post discontinuation anti-cancer therapies. A urine pregnancy test must also be performed for WOCBP at 6 months after their last dose of study treatment (ceralasertib monotherapy and ceralasertib in combination with durvalumab). Additional assessments to be performed at the time of the safety follow up are detailed in the SoA (Section 1.3).

Section 8.3.13.2 (Paternal Exposure)

Revised text

Non-sterilised male patients who intend to be sexually active with a female partner of childbearing potential should refrain from fathering a child or donating or banking sperm for 5 times the half-life (2.5 days) plus 6 months after the last dose of study treatment.

Pregnancy in a patient's partner(s) is not considered to be an AE. However, the outcome of all pregnancies (spontaneous miscarriage, elective termination, ectopic pregnancy, normal birth or congenital anomaly), occurring from the date of the first dose until 5 times the half-life (2.5 days) plus 6 months after the last dose and as indicated by previous studies (preclinical and clinical) should, if possible, be followed up and documented in the medical record and provided to the AstraZeneca Patients Safety data entry site. Consent from the partner must be obtained before the information is collected and reported to AstraZeneca via the Pregnancy Report Form.

K 1.3 Country-specific Requirements for Germany

Section 1.1 (Synopsis), Section 4.1 (Overall Design), Section 9.2 (Sample Size Determination)

Revised text

Note: "Enrolled" means a patient's, or their legally acceptable representative's agreement to participate in a clinical study following completion of the informed consent process. Potential patients who are screened for the purpose of determining eligibility for the study, but are not randomised/assigned in the study, are considered "screen failures", unless otherwise specified by the protocol.

Section 8.3 (Adverse Events and Serious Adverse Events)

Revised text

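### For the combination, AE/SAE collection ends 90 days after last dose but safety follow-up runs to 180 days, so the recording rules for days 91 to 180 conflict

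*Protocol*

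**What the plan says.** Section 8.3.1 collects AEs and SAEs from consent "throughout the treatment period and including the safety follow-up period", and gives the length of that period for the combination as "90 days after last dose of study treatment for ceralasertib and durvalumab combination". Section 8.3.2, on following unresolved events, also uses 90 days after the last durvalumab dose as its reference point.

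Section 7.1.2 schedules safety assessments at "180 days after last dose of study treatment for ceralasertib and durvalumab combination (ie, the safety follow-up visit", and the Synopsis gives the same 180 days. In the SoA, Tables 1 and 3 have a safety follow-up column headed "180 days (6 months", with full physical examination, vital signs and ECOG status marked there.

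Appendix K 1.1 (Belgium) and K 1.2 (France) replace the Synopsis and Section 7.1.2 text with "30 days after their last dose of study treatment for ceralasertib monotherapy or 90 days after last dose of study treatment" for the combination. They add a urine pregnancy test at 6 months for women of childbearing potential, and their revised SoA tables carry a 6-month column under safety follow-up.

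Section 8.3.9 makes the handling of a death depend on whether it falls "within the protocol-defined follow-up period after the administration of the last dose of study treatment", without giving a number of days.

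**The concern.** Section 8.3.1 is the section that fixes when AE and SAE collection stops. It does so by naming the safety follow-up period and giving it a length, and that length is half of what the Synopsis and Section 7.1.2 give for the same patients. The protocol therefore schedules a safety visit 90 days after its own collection window has closed. A site cannot tell from the text whether an event first arising in between is to be entered.

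This matters for a checkpoint-inhibitor combination, where late events are part of what safety follow-up is meant to capture. If some sites stop at 90 days and others continue to 180, the listings of late events will be incomplete, and unevenly so between sites. Two countries are also pointed to replacement text with the shorter figure.

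**Working it through.** No formula or stated figure has to be reproduced. The check sets the current passages side by side.

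| Place | Length given for the combination |
|---|---|
| Synopsis; Section 7.1.2 | 180 days |
| SoA Tables 1 and 3 | safety visit at 180 days (± 7) |
| Section 8.3.1 | 90 days (AE/SAE collection) |
| Section 8.3.2 | refers to 90 days after last durvalumab dose |
| K 1.1 and K 1.2 narrative | 90 days |
| K 1.1 and K 1.2 revised SoA tables | safety column at 6 months (+ 7) |
| Section 9.4.3.1 | 30 days (treatment-emergent definition, both arms) |

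**The gap.** 180 − 90 = 90 days, and 90 / 180 = 50% of the longer period. With the visit window, the last safety visit can fall on day 180 + 7 = 187.

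**Which rules reach days 91 to 180.**

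- SAEs: outside the Section 8.3.1 window, but Section 8.3.12 has all SAEs recorded in the eCRF during study conduct, whatever their causality.
- AESIs: Section 8.3.10 has all of them recorded, with no day limit.
- Examination findings: Section 8.3.5 makes new or worsened clinically relevant physical findings AEs unless they are unequivocally due to the disease, with no day limit. Sections 8.2.2 and 8.2.4 likewise turn relevant vital-sign changes and significant ECOG changes into AEs.
- Other non-serious, non-AESI events, such as symptoms the patient reports: outside Section 8.3.1, and no undated rule clearly picks them up.

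**Deaths.** Take a death of unknown cause on day 120. If the follow-up period is 180 days, Section 8.3.9 requires an SAE report as well as the Statement of Death page. If it is 90 days, Section 8.3.9 requires the Statement of Death page, and an SAE only where the death came from an event that began after the period and is judged a late-onset toxicity. The same death is handled in two ways, depending on which section supplies the length.

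**Effect on the analysis.** Section 9.4.3.1 puts only treatment-emergent AEs in the summary tables, with a cut at 30 days after last dose and before subsequent cancer therapy. Later events are only listed. An event on days 91 to 180 therefore enters no summary table under either collection window. The consequence is confined to what is collected and listed.

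**Likely origin.** The summary of changes describes the move from 90 to 180 days as "Corrected time period of follow-up for safety assessments post treatment discontinuation" and lists only the Synopsis and Section 7.1.2. This is background. The contradiction itself lies between operative sections of the current text.

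**The case against.** The strongest reply is that 90 days may be a deliberate collection window. Section 8.3.2 uses it too. In SoA Table 1 the safety laboratory tests stop at 90 days, and the 180-day visit includes the durvalumab immunogenicity sample, so a collection window shorter than the last visit is a possible design. This stands as a possibility, but the text does not say so: Section 8.3.1 uses the name of the safety follow-up period and gives it a different length. Table 3, for the sub-study, does mark laboratory tests at 180 days. The AE row of the SoA is broken in the text available, so it cannot settle where collection stops. Either intention needs an edit.

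A reader might infer more than the protocol supports:

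- That events seen at the 180-day visit have no recording rule. They have several, in Sections 8.3.5, 8.3.10 and 8.3.12. The fault is that these collide with Section 8.3.1. Late immune-mediated events in particular are AESIs and have an undated rule.
- That fatal events after day 90 go unrecorded. Section 8.3.9 documents later deaths and makes late-onset toxicity deaths SAEs, and survival follow-up continues.
- That the combination's AE rates will be under-counted. The summary tables stop at 30 days in any case, and the protocol gives no late-event rate from which to size a loss in the listings.
- That Belgian and French patients are followed for half as long as others. The Appendix K narrative says 90 days, but its tables carry the 6-month safety column. They reproduce only changed rows, so they do not show which other assessments apply there. Whether the 90 days is an intended country rule is not stated.

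**Conclusion.** The point holds as a conflict between current sections that should be resolved. For the combination, 90 days (Section 8.3.1, echoed in Section 8.3.2 and the Appendix K narrative) stands against 180 days (Synopsis, Section 7.1.2, SoA). The conflict leaves two things open: whether non-serious, non-AESI events first arising on days 91 to 180 are collected, and how Section 8.3.9 treats a death in that span.

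The span is 90 days, half of the longer period. It can concern the approximately 100 patients planned for the combination arm and the sub-study patients. About 30 of the latter are planned with evaluable biopsies, and the number enrolled is redacted. These are upper figures for the planned groups: only patients alive and still followed beyond day 90 after last dose are exposed to the ambiguity, and the protocol does not say how many that will be. The number of events affected cannot be estimated from the document.

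The consequence is uneven or incomplete listing of late events between sites. It does not change the treatment-emergent summaries or any efficacy result.

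**What to change.** Reconcile Sections 1.1, 7.1.2, 8.3.1, 8.3.2 and 8.3.9, the AE row of the SoA, and Appendices K 1.1 and K 1.2. Either of two forms would do:

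1. State one safety follow-up period for the combination and use it in every one of these places.
2. Keep a collection window shorter than the last safety visit, but say so explicitly, give the two periods different names, and state how events first seen at the last visit are recorded.

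In both cases Section 8.3.9 should name the number of days it relies on, and Appendix K should say whether its 90 days is an intended country rule, so that narrative and tables agree. Which period is right is for the sponsor to decide.

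The cost is amendment wording and, if the collection window changes, an eCRF entry window. The general SoA already contains the 180-day visit and the Appendix K tables already contain a 6-month column, so no new visit has to be created in the schedule. The summary of changes says recruitment has ended, so the change would act on patients still on treatment or in follow-up.

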8.3.2 Follow-up of AEs and SAEs

Any AEs that are unresolved at the patient's last visit in the study are followed up by the investigator for as long as medically indicated (this may be beyond the 90 days after the last

dose of durvalumab), but without further recording in the eCRF. AstraZeneca retains the right to request additional information for any patient with ongoing AE(s)/SAE(s) at the end of the study, if judged necessary.

Adverse event variables

The following variables will be collected for each AE:

- AE (verbatim)
- The date and time when the AE started and stopped
- Maximum intensity or changes in intensity
- CTCAE grade (version 5.0)
- Whether the AE is serious or not (Appendix B)
- Whether the AE is an AESI or not (Section 8.3.10)
- Investigator causality rating against the study treatment(s) (yes or no)
- Action taken with regard to study treatment(s)
- AE caused patient's withdrawal from study (yes or no)
- Administration of treatment for the AE
- Outcome

In addition, the following variables will be collected for SAEs:

- Date AE met criteria for SAE
- Date investigator became aware of SAE
- AE is serious due to
- Date of hospitalisation
- Date of discharge
- Probable cause of death
- Date of death
- Autopsy performed
- Causality assessment in relation to study procedure(s)
- Causality assessment to other medication

The grading scales found in the National Cancer Institute CTCAE Version 5.0 will be utilised for all events with an assigned CTCAE grading. For those events without assigned CTCAE grades, the recommendation in the CTCAE criteria that converts mild, moderate, and severe

events into CTCAE grades should be used. A copy of the CTCAE can be downloaded from the Cancer Therapy Evaluation Program website (http://ctep.cancer.gov).

